### **10.4.3. Unannounced meals during closed-loop**

During the 24-hour closed-loop, the subject will take two meals (evening dinner and breakfast), one snack prior to the exercise segment, and one snack 3 hours after exercise. All meals will be unannounced. This means that the subject will ingest the meal and the AP device will automatically regulate insulin delivery without being given any details about the meal. Therefore, it will react to the increase of glucose level following the meal. Based on the CGM data collected every five minutes, the AP device will quickly react to the meal and deliver correction bolus based on the predictions of future insulin. The objective is to observe the controller's ability to detect the meal and make an appropriate control action. The target glucose is to return to and remain in the range of [70-180] mg/dL during the 5 hours post-prandial and then to return to [80-140] mg/dL range afterwards.

#### **10.4.3.1. Dinner**

Approximately 2 hours ( $\pm 30$  min) after starting the closed-loop (Day 1), i.e. 6:30 pm, once the subject's glucose has been stabilized by the AP device, the subject will be given an evening meal with approximately 50 g of carbohydrates (CHO). The subject will remain under closed-loop control overnight.

#### **10.4.3.2. Breakfast**

At approximately 7:00 am ( $\pm 30$  min) on Day 2, the subject will be given a breakfast with approximately 50 g of CHO.

#### **10.4.3.3. Snack before exercising**

Just before starting the exercising segment of the trial, at approximately 11:00 am, the subject will eat a snack of approximately 16 g of CHO if his/her glucose level is  $< 120$  mg/dL.

#### **10.4.3.4. Snack after exercising**

Approximately 3 hours after starting the exercising, at approximately 2:00 pm ( $\pm 30$  min) on Day 2, the subject will eat a snack of approximately 16 g of CHO if his/her glucose level is  $< 120$  mg/dL.

### **10.4.4. Exercising**

Approximately 5 hours after the breakfast (11:00 am  $\pm 30$  min), the subject will undergo exercise for 30 minutes ( $\pm 5$  minutes) at 50% of his /

her predicted heart rate reserve (HRR). The subject will be monitored for approximately 6 hours following the end of the exercise segment or until his/her blood glucose has stabilized within the [80-140] mg/dL range. During and for 3 hours after exercise, the subject will be monitored to verify that his/her glucose level returns and remains within the range of [70-150] mg/dL.

If the subject's blood level is >270 mg/dL the subject will not go through the exercising segment of the trial, but will continue the closed-loop until the end of the 24-hour trial. Subjects whose glucose level is below 120 mg/dL at (11:00 ± 30 min) will be given 16 g CHO tablets and will not start exercise until glucose is greater than 120 mg/dL.

Exercise will be done by cycling on a recumbent stationary bicycle or by walking on a treadmill for 30 minutes (15 minutes of exercise, 5-minute break, followed by 15 additional minutes of exercise) at approximately 50% predicted heart rate reserve (HRR). HRR is calculated using the following formulas. The calculation is different for men and women.

HRR: Heart Rate Reserve

RHR: Resting Heart Rate

MHR: Maximum Heart Rate

THRX%: Target heart rate to be at X% of HRR

Smoking code: "1" if the subject is a smoker and "0" if the subject is not a smoker

Equation 1 provides the MHR for men. The Target Heart Rate is provided by equation 3.

$$\text{MHR} = 203.9 - (0.812 \times \text{Age}) + (0.276 \times \text{RHR}) - (0.084 \times \text{Weight}_{\text{kg}}) - (4.5 \times \text{smoking code}) \quad (1)$$

Equation 2 provides the MHR for women.

$$\text{MHR} = 204.8 - (0.718 \times \text{Age}) + (0.162 \times \text{RHR}) - (0.105 \times \text{Weight}_{\text{kg}}) - (6.2 \times \text{smoking code}) \quad (2)$$

Target Heart Rate for exercise (at 50%) is provided by equation 3:

$$\text{THR}_{50\%} = [(\text{MHR} - \text{RHR}) \times 50\%] + \text{RHR} \quad (3)$$

References:

Whaley MH, et al, *Predictors of over- and underachievement of age-predicted maximal heart rate*, Med Sci Sports Exerc 1992;24(10):1173-9;  
[Karvonen MJ](#), [Kentala E](#), [Mustala O](#). The effects of training on heart rate; a longitudinal study. [Ann Med Exp Biol Fenn](#). 1957;35(3):307-15;  
[Davis JA](#), [Convertino VA](#). A comparison of heart rate methods for predicting endurance training intensity. [MedSci Sports](#). 1975;7(4):295-8.

Subjects with high risks factors for cardiac disease and Type 1 diabetes, as recommended by the American Diabetes Association will be monitored with continuous electrocardiography throughout exercise to monitor for potential arrhythmias. The risks factors are:

- Age > 35 years
- Type 1 diabetes for > 15 years' duration
- Presence of any additional risks factor for coronary artery disease
- Presence of microvascular disease (proliferative retinopathy or nephropathy, including microalbuminuria)
- Peripheral vascular disease
- Autonomic neuropathy

All subjects will wear a Polar RS400 heart rate monitor. The resistance on the bicycle or the speed and grade on the treadmill will be adjusted to keep subjects close to the target heart rate.

Exercise may be discontinued at the request of the subject or at investigator discretion if there is concern for the subject's safety.

Blood glucose (YSI) will be sampled every 15±5 minutes for one hour beginning at the start of exercise. Additional YSI blood glucose values may be requested by the study physician as deemed necessary for safety.

Exercise will be discontinued and the subject will be given 16 mg CHO if the system predicts unavoidable impending hypoglycemia as determined by the HMS (i.e. when CGM glucose level is predicted to be <70 mg/dL in the following next 15 min). Treatment with 16 mg CHO may be repeated as necessary.

If the subject feels hypoglycemic subject will perform finger stick and YSI measurement will be taken. If YSI value below 60 mg/dL, juice or

glucose tablets will be used to return the glucose to  $>80$  mg/dL and exercise may be discontinued. Closed-loop will be discontinued. This will mark the end of the trial for this subject.

Following the exercise segment, the subject will be monitored for approximately 5-6 hours (end of the 24-hour period). During that time, the insulin delivery for the subject will continue to be controlled by the AP device. The patient may have a snack of 16 g CHO approximately 3 hours after the start of exercise. The patient will not be discharged until blood sugar value, based on YSI is  $>90$  mg/dL for at least an hour.

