#### **1.4. Control algorithm**

The control algorithm is unique to this application: it combines a zone-Model Predictive Control (MPC) algorithm with the added safety feature of the Health Monitoring System (HMS) which provides warnings and notifications of impending hypoglycemia to request outside intervention, such as absorption of fast acting glucose. The notification is not only available to the subject via the AP device, but also to the physician or another person who could be located remotely in the future (this IDE exclusively takes place in the clinical research setting in presence of a physician). The HMS algorithm uses the same CGM data as the zone-MPC control algorithm but utilizes a separate algorithm for trending and predictions of future glucose values. Using a redundant and independent algorithm is an important safety feature of the overall AP device. The HMS will send a warning to the AP device and a text message to the attending physician (present at all times) whenever it predicts a glucose value below 70 mg/dL within the next 15 minutes. The warning will include a recommendation to give the subject approximately 16 g of carbohydrates. The warning must be acknowledged for the pop-up window to close. The acknowledgement gives the choice to “accept” or “ignore” the warning and recommendation.

The zone-MPC control algorithm is at its core a Model Predictive Control (MPC), which incorporates an explicit model of human T1DM glucose-insulin dynamics. The model is used to predict future glucose values and to calculate future controller moves that will bring the glucose profile into the desired range. Software constraints ensure that insulin delivery rates are constrained between minimum and maximum values. The first insulin infusion (out of  $n$  steps) is then implemented. At the next time step,  $k + 1$ , the process is repeated based on the new measured glucose value and the last insulin rate. The algorithm adjusts insulin delivery automatically to achieve and maintain the patient’s glucose level within a predetermined safe range: 80-140 mg/dL. The only variable that may be adjusted between subjects is the *responsiveness factor* which is the ration of  $Q/R$ . It can be described as the agility of the control algorithm to respond to

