YSI + finger stick CONTOUR® EZ	Hypoglycemia: BG<70 mg/dL per YSI Or if AP device (CGM) predicts <70 mg/dL in the following 15 min	Every 15±5 min until YSI >80 mg/dL
YSI + finger stick CONTOUR® EZ	Hyperglycemia: BG>400 mg/dL	Every 15±5 min Until YSI<300 mg/dL
YSI + finger stick CONTOUR® EZ	During exercise	Every 15±5 min and for 1 hour after starting exercise

The AP device includes multiple visual and auditory alarms that are embedded into the APS© software should the system malfunction. The control algorithm also includes intrinsic safety limits that trigger alarms should the patient’s glucose level go too high or too low and which prevents the system from delivering too much insulin.

Should the HMS predict that the glucose level is going to be <70 mg/dL in the next 15 min, the system will alert on the AP device and send a redundant text message to a predefined list of people, which in this study will be only the physician (who will be next to the subject in this study) to notify the subject to eat 16 g of CHO. All warnings issued by the HMS will be documented.

To prevent dehydration secondary to hyperglycemia, the subject will be allowed to consume sugar free beverage during the trial if he/she is thirsty.

Each adverse event will be graded as mild, moderate, or severe as described by [Table 15–1](#) ~~Table 9–4~~. Should there be any Serious Adverse Event or Unanticipated Adverse Device Effect, immediate action for the safety and welfare of the patient will be taken. An investigation will be promptly conducted and reported to the safety

officer of the IRB. All adverse events will be documented as described in section [159](#).

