#### 11.4. **Stopping rules**

##### 11.4.1. **Criteria for individual subject withdrawal**

The termination of a subject from the study will be documented in the subject source documents and on the CRF. The reason for the termination and possible following effects must be documented. Subjects that have discontinued participation will not be replaced. Should a subject be lost-to-follow-up (LTF), i.e. no return for the on-site 24-hour closed-loop after enrollment, a reasonable effort will be made to contact the subject to determine why the subject failed to return. Any investigator-decided outside intervention will trigger termination of the trial for the subject. If the investigator treats the subject with 16 g of carbohydrates following the recommendation of the HMS, then the trial will not be terminated, this is anticipated and part of the trial. If a trial is terminated, the same subject may be rescheduled and the trial repeated. Rules for terminating a visit for an individual subject are as follows (glucose levels measured by YSI).

- Outside intervention (bolus or carbohydrate treatment) from the investigator that did not follow recommendation from HMS.
- Gross system malfunctions such as:
  - Pump failure
  - Failure of both study sensors
  - System or controller malfunctions that may have an impact on the safety of the subject
- Any correction bolus initiated by the investigator.
- Glucose YSI > 250 mg/dL for more than 2 hours and blood ketones exceed 1.0 mmol/L.
- Subject develops nausea, vomiting, or abdominal pain and blood ketones exceed 1.0 mmol/L.
- Glucose YSI > 350 mg/dL with decreased sensorium with or without emesis.
- Glucose level YSI > 400 mg/dL at any point if the investigator decides to treat with a correction bolus.

- Glucose YSI < 60 mg/dL without having received a HMS warning
- Glucose YSI < 50 mg/dL.
- Severe Hypoglycemia or Hyperglycemia as defined by Table 9-2.
- The subject or physician requests the trial be stopped.
- Failure of YSI equipment.
- Subject withdraws his/her consent.
- Adverse Event which necessitates termination of the study as decided by the investigator, such as DKA.
- Protocol violation: subject is no compliant with procedures, becomes pregnant, violates study entry criteria, or use unacceptable medication.

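### Section 10.4.4 states the carbohydrate treatment for a Health Monitoring System (HMS) warning during exercise as 16 mg, twice, while every other section that states an amount for HMS-triggered carbohydrate gives 16 g

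*Combined protocol and SAP*

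**What the plan says.** Section 10.4.4 (Exercising) covers what happens if the HMS predicts a low while the subject is exercising: "Exercise will be discontinued and the subject will be given 16 mg CHO if the system predicts unavoidable impending hypoglycemia". It defines the trigger as "when CGM glucose level is predicted to be <70 mg/dL in the following next 15 min", and then adds: "Treatment with 16 mg CHO may be repeated as necessary".

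The same warning is described elsewhere with a different unit:

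- Section 1.4 (Control algorithm) says that the HMS alerts "whenever it predicts a glucose value below 70 mg/dL within the next 15 minutes", and continues: "The warning will include a recommendation to give the subject approximately 16 g of carbohydrates".
- Section 10.4.2.1 (On-going monitoring) says that the alert is sent "to notify the subject to eat 16 g of CHO".
- Table 10-2 (section 10.4.2.3, Safety), in the row for a CGM prediction below 70 mg/dL in the next 15 minutes, gives 16 g of oral carbohydrate and says that the session goes on.
- Section 11.4.1 (individual withdrawal) says: "If the investigator treats the subject with 16 g of carbohydrates following the recommendation of the HMS, then the trial will not be terminated".

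Some places refer to HMS-directed carbohydrate without naming an amount: the synopsis in the Executive Summary, the text of section 10.4.2.3, and the Table 10-2 row for symptoms with YSI glucose between 60 and 70 mg/dL.

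**The concern.** Two written amounts exist for one alert, and the section that staff would open for the exercise segment carries the one that differs from the rest. The statement is an instruction to treat, and the amount it names is also the one to be repeated. Nothing in the documents says that an alert during exercise calls for a different amount from an alert at any other time.

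Exercise is one of the three challenges in section 2.1, and the background on the predecessor study (IDE G110093) describes falls in glucose after exercise. At stake is a clear instruction at the moment of an impending low. A second matter is the record: section 10.4.2.3 requires all actions, including carbohydrate taken, to be documented in the CRF. With two amounts in the protocol, no single treatment given during exercise can be compliant with both texts.

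**Working it through.** No sample-size, power or error-rate formula applies. The check has four steps.

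**1. Is the trigger the same?** Section 10.4.4 speaks of unavoidable impending hypoglycemia, which could suggest a separate and more severe condition. It then defines the term as an HMS determination: CGM glucose predicted below 70 mg/dL within 15 minutes. Sections 1.4 and 10.4.2.1 and the Table 10-2 row use the same threshold and the same horizon. Section 11.4.1 refers to the HMS recommendation, which is the one that section 1.4 describes. The trigger is therefore the same.

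**2. What amount does each place state?**

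| Place | Amount for the HMS warning |
|---|---|
| 10.4.4, first statement | 16 mg |
| 10.4.4, repeat treatment | 16 mg |
| 1.4 | about 16 g |
| 10.4.2.1 | 16 g |
| Table 10-2, prediction row | 16 g |
| 11.4.1 | 16 g |

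That is two statements in milligrams, both in section 10.4.4, against four in grams.

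**3. How large is the difference?** 16 g = 16 × 1000 mg = 16,000 mg, and 16,000 mg / 16 mg = 1000. Equivalently, 16 mg = 16 / 1000 g = 0.016 g.

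**4. Could it be an error in reading the PDF?** That is unlikely. The milligram unit appears in two consecutive sentences, while the same section shows grams in two other places. One is the pre-exercise rule, under which subjects below 120 mg/dL "will be given 16 g CHO tablets and will not start exercise until glucose is greater than 120 mg/dL". The other is the snack about three hours after exercise starts. Those two are separate occasions from an HMS warning, so they do not themselves contradict the 16 mg statements. They show only that the gram unit is legible in that section.

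**The case against.** The strongest reply is that staff are unlikely to act on section 10.4.4 alone. The HMS warning itself carries a recommended amount in a window that must be acknowledged (section 1.4). The synopsis has the investigator follow that recommendation. Section 10.4.2.3 points to Table 10-2 for safety actions, and that table states an amount for this trigger. A physician is present throughout, and YSI glucose is sampled about every 15 minutes for an hour from the start of exercise. Alerts in this window may also be rare: exercise is not to begin until glucose is above 120 mg/dL, and the background section reports no HMS alert during exercise in the predecessor study. All of this stands and lowers the practical risk. It does not settle which text governs, and the predecessor study did not use inhaled insulin, so its experience does not show that the alert will not occur here.

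The reply also bears on three stronger readings that a reader might infer and that the documents do not support.

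- *That a treatment other than 16 g would end the session.* Section 11.4.1 does name 16 g when it says that the trial continues. However, its listed rule turns on whether the intervention followed the HMS recommendation. Section 10.4.2.3 keeps the subject in the trial after HMS-prompted carbohydrate without naming an amount, and section 16.1 counts such intervention as a success, also without an amount.
- *That all 12 to 20 subjects are affected.* Only those with an HMS warning during exercise are.
- *That the primary measures depend directly on the discrepancy.* Table 16-2 includes time in 70-150 mg/dL during exercise and for 3 hours after it. The discrepancy could affect these only if an alert occurs in the exercise segment and the amount given differs because of the conflicting text.

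**Conclusion.** The contradiction is real and needs correcting. For one HMS trigger, section 10.4.4 states 16 mg twice, and the four other places that state an amount give 16 g, a factor of 1000. It matters because it lies in an operative hypoglycemia instruction and not in background text.

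Its reach is limited to subjects who have an HMS warning during exercise, and other parts of the protocol reduce the chance that it changes what is done. No termination rule clearly turns on it, and neither the sample size nor any other statistical calculation is affected. The conclusion assumes that the extracted text shows the units as printed, which the repetition within section 10.4.4 supports. A reader might take the count of four against two as settling which amount is intended. A count of statements is not evidence of intent, and this review takes no position on it.

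**What to change.** Reconcile the two statements in section 10.4.4 with sections 1.4, 10.4.2.1 and 11.4.1 and Table 10-2, so that one amount and one unit apply to HMS-triggered carbohydrate throughout. The sponsor should state which amount is intended. If a different amount during exercise is meant, section 10.4.4 should say so explicitly and the other places should refer to it. Any staff instructions or CRF pages that carry the amount should be checked for agreement; they were not among the documents available here.

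The cost is a short text correction through the usual protocol-change route. It requires no change to the design, data collection or analysis.

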#### **10.4.5. Discharge from the CRC**

At the end of the 24-hour period and once the glucose level of the subject has stabilized within the desired zone ( $>90$  mg/dL for at least 1 hour), the AP device will be disconnected. The IV line and the two CGMs will be removed. The subject will be connected to his/her own insulin pump. The investigator or study staff will verify that the insulin pump of the subject has been restarted successfully. Glucose check will be performed after new infusion set or the pump of the subject has been inserted, as per standard care. Subject will return all supplies to study staff. On the subject's blood glucose is  $>90$  mg/dL and  $<180$  mg/dL with ketones  $<0.6$  mmol/L, the subject will be discharged from the CRC.

This marks the end of the study day after using the AP device for approximately 24-hour (as a closed-loop).

#### **10.5. Follow-up call**

A brief contact with the subject, typically by phone, will take place within 24 hours ( $\pm 12$  hours) to verify that the subject has no further questions or has any problems related to his/her participation in the study. The contact will be documented in the subject file.

## **11. SELECTION AND WITHDRAWAL OF SUBJECTS**

Twelve to twenty subjects will be enrolled in the study.

### **11.1. Inclusion criteria**

To be eligible for the study, a subject must meet the following criteria:

- Clinical diagnosis of type 1 diabetes for at least one year and using an insulin pump for at least 6 months with commercially available rapid acting insulin

- The diagnosis of type 1 diabetes is based on the investigator's judgment; C peptide level and antibody determinations are not needed.
- Age 21 to 65 years
- For females, not currently known to be pregnant or nursing
- HbA1c between 5.0% and 10%, as measured with DCA2000 or equivalent device
- Willing to perform the calibration of the study CGMs using a finger stick only and willing to follow instructions for insulin pump and CGM wear.
- Willing to use the study CGM and study insulin pump during closed-loop.
- Able to and agrees to avoid the following medication starting 24 hours before sensor wear through completion of CRC visit: acetaminophen, prednisone, and pseudoephedrine.
- Forced expiratory volume in 1 second (FEV1)  $\geq$  70% Third National Health and Nutrition Examination Survey (NHANES III) predicted
- Forced vital capacity (FVC)  $\geq$ 70% NHANES III predicted
- Forced expiratory volume in 1 second as a percentage of forced vital capacity (FEV1/FVC)  $\geq$  NHANES III lower limit of normal (LLN)
- An understanding of and willingness to follow the protocol and sign the informed consent.

### **11.2. Exclusion criteria**

The presence of any of the following, the subject will be excluded from the study:

- Pregnancy (as determined by a positive blood pregnancy test performed in females of childbearing capacity during screening visit and urine test at time of admission for in-patient visit) or nursing mother.
- Diabetic ketoacidosis in the past 6 months prior to enrollment requiring emergency room visit or hospitalization
- Severe hypoglycemia resulting in seizure or loss of consciousness in the 12 months prior to enrollment
- Current treatment for a seizure disorder;
  - Subjects with a history of seizures may be included in the study if they receive written clearance from their neurologist

- Cystic fibrosis
- Active infection
- A known medical condition that in the judgment of the investigator might interfere with the completion of the protocol such as cognitive deficit.
- Mental incapacity, unwillingness or language barriers precluding adequate understanding or co-operation, including subjects not able to read or write.
- Coronary artery disease or heart failure.
  - Subjects with a history of coronary artery disease may be included in the study if they receive written clearance from their cardiologist
- Presence of a known adrenal disorder
- Active coronary artery disease or heart failure
- Active gastroparesis
- If on antihypertensive, thyroid, anti-depressant or lipid lowering medication, lack of stability on the medication for the past 2 months prior to enrollment in the study
- Uncontrolled thyroid disease
  - Adequately treated thyroid disease and celiac disease do not exclude subjects from enrollment
- Abuse of alcohol
- A recent injury to body or limb, muscular disorder, use of any medication, any carcinogenic disease, or other significant medical disorder if that injury, medication or disease in the judgment of the investigator will affect the completion of the exercise protocol
- Current use of a beta blocker medication
- Laboratory results:
  - Hematocrit < 30% or >55%
  - A1C > 10%
  - Abnormal liver or renal function (Transaminase >2 times the upper limit of normal, Creatinine > 1.5 mg/dL)
  - Labs drawn at screening visit or within one month prior to screening (for other purposes) will suffice for enrollment purposes related to hematocrit

- Subject has skin conditions that, in the determination of the investigator, would preclude wearing the study devices (infusion set and sensor), in the abdomen. Examples include but are not limited to: psoriasis, burns, scarring, eczema, tattoos, and significant hypertrophy at sites of device wear; any known allergy to medical adhesives.
- Currently on long-term treatment using prednisone.
- If subject had been on short term treatment of prednisone, defer enrollment until underlying condition and prednisone treatment have resolved.
- Allergy to study drug, food or other study material.
- History of asthma, COPD (chronic obstructive pulmonary disease), or any other clinically relevant chronic lung disease.
- Respiratory track infection within 4 weeks before screening.
- Clinically significant screening ECG, physical examination, laboratory test, or vital sign abnormality.
- Exposure to any investigational drug within 30 days.
- History of malignancy within the 5 years before screening (other than basal cell carcinoma).
- Inability, in the opinion of the investigator, to adequately inhale Technosphere® Insulin Inhalation Powder.
- Abnormal spirometry.
- Currently smoking or discontinued smoking (including cigarettes, cigars, pipes) over the past 6 months.
- Highly sensitive to insulin: insulin-to-carbohydrate ratio I:C > 1:12
- Current participation in another investigational trial (unless participation to original protocol of IDE G110093) or has previously participated to this study.

